3.0 Study Design

Cohort study of children tested with the REBIScan device followed by a vision examination.

The data will be collected using one PVS device during the child's regularly scheduled examination or on a single examination on another day at a pediatric center within the KP system. The additional examination following PVS will consist of an eye examination by a pediatric ophthalmologist. Parents and patients will be given the opportunity to complete all of the study testing during their initial visit.

4.0 Device Information

4.1 Description of Device

The Pediatric Vision Scanner is a binocular scanner, which detects fixation in both eyes simultaneously. It detects fixation of the human eye remotely by scanning the eye with an annulus of low-intensity, polarized laser light. Previous studies have shown that it is capable of detecting strabismus in children as young as 2 years of age. Additional studies showed it could detect amblyopia in apparently straight-eyed subjects due to the high accuracy of fixation detection. REBIScan has built hand-held prototypes for clinical testing.

To allow easy operation, the PVS was equipped with a simple two-button interface and binary red-light/green light output. The device displays a binocularity score to indicate the accuracy of fixation on an internal target. A binocularity score of 60% and above (with 2 green lights) gives a "pass" recommendation; lower binocularity (with one or two red lights) results in a "refer" recommendation.

For PVS data collection, the child will be seated approximately 40 cm from the instrument fixation target. Room lights will be dimmed to enhance interest in the illuminated target and to increase pupil size. A background measurement will be obtained with eyes closed, and subtracted from subsequent readings to improve the signal to noise ratio. Data collection will last between 2.5 and 5 seconds of attention to the fixation target. Results will be recorded on the data form, but the patient, parents, and ophthalmologists will not be informed of the results.

The PVS can be operated by lay users, but some training is required, and it is possible that some individuals may have difficulty following the protocol. The Contact PI has extensive experience training users of all backgrounds in use of the device. Regular site visits by REBIScan study personnel will ensure that testing is being performed according to instruction and allow for correction of any observed problems.

In the event that meaning of the results is conveyed to a participant, caregivers, or providers, the participant will be excluded from the study and recruitment will continue until at least 300 participants who are eligible for analysis have been tested.

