5.3 Withdrawal Criteria

If a participant is unable to complete the PVS scan due to lack of cooperation, such as refusing to open one's eyes or take further direction, then the inability to participate will be recorded, and the participant will be excluded from the study, post-hoc, and not considered a part of the 300-participant cohort.

A participant may also be excluded from the study post-hoc if study personnel vocally share results of the PVS with the participant, parent, or provider prior to the Ophthalmic Examination. General observation of device indicator lights by the participant, parent, or provider is not justification for exclusion.

Finally, a participant can be excluded post-hoc if unable to complete the ophthalmic examination.

All excluded participants will be documented in the final analysis to compare how many participants were unable to perform the screening. Post-hoc exclusions at this stage will be determined by the study coordinator prior to review of the PVS screening results.

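### Sections 4.1 and 5.3 give different rules for excluding children whose PVS result was disclosed, and excluding on disclosure can bias sensitivity and specificity in a direction the protocol does not fix

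*Protocol*

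**What the plan says.** Section 4.1 plans for non-disclosure: "the patient, parents, and ophthalmologists will not be informed of the results". If disclosure happens anyway, exclusion is mandatory: "In the event that meaning of the results is conveyed to a participant, caregivers, or providers, the participant will be excluded from the study". The child is then replaced: "recruitment will continue until at least 300 participants who are eligible for analysis have been tested". No time limit is given, and it does not matter who conveyed the result or how.

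Section 5.3 words the rule differently: "A participant may also be excluded from the study post-hoc if study personnel vocally share results of the PVS with the participant, parent, or provider". The sentence goes on to limit this to disclosure before the ophthalmic examination. Seeing the lights is exempt: "General observation of device indicator lights by the participant, parent, or provider is not justification for exclusion".

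Section 5.3 also has two safeguards. One concerns who decides and when: "Post-hoc exclusions at this stage will be determined by the study coordinator prior to review of the PVS screening results". The other concerns reporting: "All excluded participants will be documented in the final analysis to compare how many participants were unable to perform the screening".

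Section 10.0 masks the examining ophthalmologist to the PVS result. Section 12.0 names sensitivity and specificity as the outputs. Section 2.2 sets a 10% limit on a false positive rate, which it then describes as the share of unaffected children among those who screened positive.

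**The concern.** The two sections define different analysis sets. A child whose parent was told after the diagnosis had been recorded is out under section 4.1 and in under section 5.3. A child told by study personnel before the examination must go under one section and may stay under the other.

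The exclusion is also triggered by an event that comes after the index result and can depend on it. A parent may ask about a red light, or staff may reassure after a green one. If the chance of disclosure differs between *refer* and *pass*, the analysed children are a selected mix of results. Recruiting on to 300 restores the number but not the mix, because the replacements pass through the same filter.

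The safeguards in section 5.3 do not reach this. Deciding before the PVS results are reviewed masks the decision, not the event that triggers it, and a result spoken aloud may already be known to the coordinator. The stated purpose of documenting exclusions is to count children who could not do the test. Nothing in the protocol has disclosure recorded against the PVS result, so any imbalance could go unseen.

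**Working it through.** **The plan's own figures (section 12.0).** 300 × 5% = 15 affected and 285 unaffected. At 92% sensitivity, 15 to 20 cases give 13.8 to 18.4 detected, matching the stated 14 to 18. False referrals are 0.13 × 285 = 37.05 at 87% specificity, within the stated ceiling of 45. At 82% they are 0.18 × 285 = 51.3, which exceeds it. The ceiling of 45 (15% of 300) therefore does not follow from the anticipated 82%. This is a side observation, and the steps below do not use the ceiling.

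**Inputs.** Published sensitivity and specificity are 97% and 87%; the lower anticipated values are 92% and 82% (section 12.0). Let d_r and d_p be the probabilities that a *refer* or a *pass* result is disclosed and the child excluded. The documents give neither, so every value below is an assumption.

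**Formulas.** With f = 1 − specificity and Se = sensitivity, the analysed values are:

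- f′ = f(1 − d_r) / [f(1 − d_r) + (1 − f)(1 − d_p)]
- Se′ = Se(1 − d_r) / [Se(1 − d_r) + (1 − Se)(1 − d_p)]

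**Results.**

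| d_r | d_p | f′ from 13% | f′ from 18% | Se′ from 97% | Se′ from 92% |
|---|---|---|---|---|---|
| 10% | 2% | 12.1% | 16.8% | 96.7% | 91.4% |
| 20% | 2% | 10.9% | 15.2% | 96.4% | 90.4% |
| 30% | 2% | 9.6% | 13.6% | 95.8% | 89.1% |
| 20% | 20% | 13.0% | 18.0% | 97.0% | 92.0% |
| 5% | 20% | 15.1% | 20.7% | 97.5% | 93.2% |

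For example, in the first row 33.345 / (33.345 + 242.991) = 12.1%, from 37.05 × 0.9 and 247.95 × 0.98.

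**Disclosure needed for 1 − specificity to reach 10%.** Setting f′ = 0.10 gives 1 − d_r = (0.10/0.90) × [(1 − f)/f] × (1 − d_p). With d_p = 2%:

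- Specificity 87%: (1/9) × (0.87/0.13) × 0.98 = 0.729, so d_r is about 27%. That is about 14 of the 51.6 *refer* results expected per 300 tested (14.55 true + 37.05 false).
- Specificity 82%: (1/9) × (0.82/0.18) × 0.98 = 0.496, so d_r is about 50%. That is about 33 of 65.1 *refer* results (13.8 + 51.3).

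**The rate spelled out in section 2.2.** Unaffected among screen-positives = FP(1 − d_r) / [FP(1 − d_r) + TP(1 − d_r)] = FP/(FP + TP), since (1 − d_r) cancels. It is 37.05/51.6 = 71.8% at the published values and 51.3/65.1 = 78.8% at the lower ones, whatever the disclosure rates.

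**Scale against sampling error.** The standard error of 13% in 285 children is √(0.13 × 0.87/285) = 2.0 points, and of 92% in 15 cases √(0.92 × 0.08/15) = 7.0 points. The shifts at d_r = 10% and d_p = 2% (0.9 and 0.6 points) are well inside these.

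**The case against.** The strongest reply is that disclosure is a protocol breach which training and regular site visits are meant to prevent, so few children should be affected. Excluding them is also a defensible way to protect masking. Scan and examination normally fall on the same day (section 9.0), so a parent who has been told can repeat the result to the ophthalmologist. Where acuity cannot be obtained, the diagnosis rests on clinical judgement (section 10.0), which an unmasked examiner could let the result influence. This stands: some exclusion is justified, and the effect is small unless disclosure is common.

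A rule that excludes only when the examiner was told can itself depend on the result. That also stands, and is why analyses on both sides of the rule are needed.

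Breakdowns and sensitivity analyses may be in an analysis plan that is not shown. That is fair for the tables. It does not cover the conflict between sections 4.1 and 5.3, or recording disclosure when it occurs, which cannot be added reliably afterwards.

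A reader might infer that the rule drops every child whose family is told, mostly those with *refer*, and so pushes the hypothesised false positive rate towards its 10% limit. The documents do not support this. *Every child* fits section 4.1 but not section 5.3, which also exempts seeing the lights. Nothing says that *refer* is voiced more often. And the rate spelled out in section 2.2 does not move under selection on the PVS result alone.

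**Conclusion.** The contradiction between sections 4.1 and 5.3 can be read directly from the text and needs resolving. The bias is conditional: excluding on disclosure distorts sensitivity and specificity only if disclosure differs between *refer* and *pass*, and the documents give neither rate. Under the assumed rates, 1 − specificity moves from 13.0% to between 9.6% and 15.1% at the published values, and from 18.0% to between 13.6% and 20.7% at the lower ones. Reaching 10% would take frequent disclosure of *refer* results. The statement that the section 2.2 proportion is unaffected assumes that disclosure depends on the PVS result only; if it also differed between affected and unaffected children with the same result, the cancellation would fail. This is a cheap improvement, not a defect that undermines the study.

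**What to change.** - Put one rule in sections 4.1 and 5.3. The main analysis keeps every child with a completed scan and examination whose examiner was still masked when the diagnosis was recorded. Disclosure leads to exclusion only if the examiner learned the result before that point.
- Record disclosure on the data form: whether it happened, to whom and when.
- Tabulate disclosure and all exclusions by *pass* and *refer*.
- Report sensitivity and specificity twice more: without any disclosed child, and with all disclosed children who completed both tests.

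The cost is rewording two sections, a short entry on the form and two extra runs of the same analysis; no child is tested again. The downside is that some children with possible indirect unmasking stay in the main analysis, and the remaining exclusion may still depend on the result. The two sensitivity analyses show how much either matters.

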4.2 IND/IDE Number

The FDA has determined that the Pediatric Vision Scanner is a non-significant risk (NSR) device because it does not meet the definition of a significant risk (SR) device under § 812.3(m) of the investigational device exemptions (IDE) regulation (21 CFR 812). As a result, an IDE application is not required to be submitted to, or approved by, the FDA for a NSR study.

4.3 Device Supplier Information

During Phase II, REBIScan will provide one unit upon study commencement, and will have a second device available for use, if necessary and mutually agreed upon, by study personnel.

5.0 Selection and withdrawal of subjects

5.1 Inclusion Criteria

Children who present to the pediatric clinic will be invited to participate in the study if they are aged older or equal to 2 years of age, and less than 6 years of age.

5.2 Exclusion Criteria

- Developmental delay or cognitive deficit
- Visually obvious ocular conditions that would warrant specialist referral

- The PVS is designed to identify patients requiring referral to a specialist for evaluation of amblyopia or strabismus. Patients with these conditions often have no external signs of an abnormality, and thus will not be referred if they are not tested. In contrast, children with, for example, ptosis, periocular masses, ocular discharge, active conjunctivitis, corneal scarring, abnormal pupils, anterior polar or total cataracts, orbital cellulitis, ocular trauma, or large-angle strabismus will need to be referred to a specialist regardless of the results of the PVS scan. For this reason there is no benefit to enrolling such patients in a study of how effective the PVS is at referring children with amblyopia and strabismus (including microstrabismus.) Each of these excludable conditions would be easily recognized by a pediatrician.

5.3 Withdrawal Criteria

If a participant is unable to complete the PVS scan due to lack of cooperation, such as refusing to open one's eyes or take further direction, then the inability to participate will be recorded, and the participant will be excluded from the study, post-hoc, and not considered a part of the 300-participant cohort.

A participant may also be excluded from the study post-hoc if study personnel vocally share results of the PVS with the participant, parent, or provider prior to the Ophthalmic Examination. General observation of device indicator lights by the participant, parent, or provider is not justification for exclusion.

Finally, a participant can be excluded post-hoc if unable to complete the ophthalmic examination.

All excluded participants will be documented in the final analysis to compare how many participants were unable to perform the screening. Post-hoc exclusions at this stage will be determined by the study coordinator prior to review of the PVS screening results.

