6.0 Stratification / Descriptive Factors / Randomization Scheme

KP staff will manage all recruitment efforts for participation, as well as completing consent and data forms for all enrollees. Children who present to the pediatric clinic and meet the inclusion criteria will be invited to participate in the study until 300 participants have been enrolled and are eligible for analysis. The researcher will describe the study to their parents and obtain informed consent. The consent form will be written at a level simple enough for parents to read meaningfully and for older children to understand.

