The test consists of a book with 3 pairs of pages. Each pair contains two sets of four random dot shapes (one is blank, the other three contain shapes) that can be named or matched to the easily visible black-and-white shapes on the other side of the book. Page 1 is presented first to test 200 arcsec and 100 arcsec levels of disparity. If the child is able to correctly identify two of three shapes at both of these disparity levels, Page 2 is presented next to test 60 arcsec and 40 arcsec disparity. If the child is unable to identify two of the three shapes at 200 arcsec disparity, Book 3 is presented instead to test 800 arcsec and 400 arcsec disparity. Stereoacuity is defined as the smallest disparity at which the child is able to correctly identify at least two of three shapes. Visual acuity will be measured monocularly using a standard eye chart at standard testing distance. An adhesive patch will cover one eye during acuity testing. Cover-uncover and alternate cover testing will be performed at distance and at 40 cm (the testing distance of the PVS device) by asking the subject to focus on a letter target or sticker while alternately covering

the two eyes; the observer watches for movement of the eyes as cover alternates. A cycloplegic refraction will be performed on all children.

KP study personnel will compile all data forms and KP biostatisticians will perform the statistical analysis.

Feasibility acceptance is for non-ophthalmic personnel to perform PVS testing in less than 2 minutes, and with fewer than 3 attempts, on 90% of the enrolled cohort.

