11.0 Data collection and monitoring

Name, date of birth, and medical record number will be recorded on an enrollment form (see appendix), which will also include a numeric study identification code. Subject confidentiality will be maintained by utilizing this code in lieu of identifiable subject information. A study identification log will be utilized as the only link between a subject's study identification code and their identifiable information such as name and medical record number. The study identification log will be kept in a locked file accessible only to study staff for the purposes of enrolling subjects.

Data forms will be completed for each PVS screen. Key data collected include PVS binocularity score and total time spent testing. Timing will begin once the study subject is in the chair and ready, and will conclude upon placing instrument down after all steps to acquire measurement have been completed. Data acquisition procedures and collection updates will be reviewed during site visits.

Data collected on case report forms will be entered into a database periodically. The data capture screens will be designed to capture the information from the data collection case report forms. System security will be maintained by requiring user authentication to gain access to the file on the site's private secure network. Only authorized users will be permitted access to the data files. Only de-identified information will be transferred to REBIScan. All study data that was agreed to be shared with REBIScan will be given only to authorized study personnel in compliance with IRB and HIPAA requirements.

Subject Safety and Data Monitoring

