12.0 Statistical considerations

This study is the second of a two-phased study. The first phase was a pilot and feasibility study to understand the utility of using the PVS device within Kaiser Permanente. This second phase is to determine the sensitivity and specificity of the device and its feasibility for widespread deployment in a primary care setting.

The collected data will generate patient demographic and clinical descriptives to describe the study population.

The outputs that will be calculated are sensitivity and specificity for detecting amblyopia or strabismus. The current published data on PVS sensitivity and specificity is 97% and 87% respectively. Error! Bookmark not defined. It is anticipated that sensitivity will be within 5% of the published results; that is, 92% sensitivity and 82% specificity (contained within the calculated 95% confidence intervals.) Assuming a 5% prevalence rate of the conditions, in a sample size of 300 children we anticipate 15-20 children presenting with amblyopia or strabismus; therefore we expect to identify 14-18 cases, while having no more than 45 false referrals.

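### The 90% feasibility criterion rests on an undefined enrolled cohort, and Section 5.3 applied literally removes children who would not cooperate with the scan before feasibility is judged

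*Protocol*

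**What the plan says.** Protocol Section 12.0 gives this phase two aims: to "determine the sensitivity and specificity of the device and its feasibility for widespread deployment in a primary care setting". The only acceptance rule for the second aim is in Section 10.0: non-ophthalmic staff should be able to do the test "in less than 2 minutes, and with fewer than 3 attempts, on 90% of the enrolled cohort". The protocol does not define *enrolled cohort*.

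Section 5.3 deals with a child who cannot complete the scan through lack of cooperation, for example by refusing to open the eyes. The failure is noted on the study record, and the rule for the child's place in the study then reads: "the participant will be excluded from the study, post-hoc, and not considered a part of the 300-participant cohort". The same section adds: "All excluded participants will be documented in the final analysis to compare how many participants were unable to perform the screening".

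Section 6.0 invites children "until 300 participants have been enrolled and are eligible for analysis". Section 4.1, on children excluded because results were disclosed, says "recruitment will continue until at least 300 participants who are eligible for analysis have been tested". Section 6.0 also has staff complete consent and data paperwork for every enrollee.

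**The concern.** A child of 2 to 5 years who will not be scanned is a plain instance of the scan not being feasible. Section 5.3 removes that child from the study and from the only cohort to which the protocol gives a size, and Section 6.0 fills the place with another child. If the 90% is then taken over those 300, the exclusion has selected on the outcome being judged. A child who completes slowly, or needs three or more attempts, counts against the device, while a child who cannot be scanned at all does not.

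At stake is the pass or fail statement on feasibility. The same data can support opposite statements depending on which cohort the analyst uses. The protocol fixes both the threshold and the exclusion rule but does not connect them.

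**Working it through.** **The two readings**

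- *Narrow:* the enrolled cohort is the 300. Support: Section 5.3 excludes from the study as well as from the 300, and Section 6.0 recruits on until 300 remain.
- *Wide:* the enrolled cohort is everyone enrolled. Support: Section 10.0 says enrolled and not analysable; Section 6.0 treats eligibility for analysis as a further condition on top of enrolment and refers to all enrollees; Section 4.1 also describes the 300 as those eligible for analysis.

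Section 5.3 requires the number excluded to be documented but does not say whether it enters the 90%.

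**Inputs**

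- Threshold 90% (Section 10.0).
- Completers: 300 (Sections 5.3 and 6.0).
- Non-completers *k*: not given in the protocol, so assumed and varied.
- No other exclusions (a simplification).

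The 90% is a chosen cut-off with no derivation behind it, so there is no protocol figure to reproduce.

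**Formulas**

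- Narrow: successes needed = 0.9 × 300 = 270, whatever *k* is.
- Wide: N = 300 + *k*; successes needed = 0.9 × N rounded up; a bare narrow pass becomes 270/N.
- The readings disagree when successes lie from 270 to one below the wide requirement.

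| *k* | N | *k*/N | 270/N | Needed, wide | Readings disagree for |
|---|---|---|---|---|---|
| 3 | 303 | 1.0% | 89.1% | 273 | 270-272 |
| 6 | 306 | 2.0% | 88.2% | 276 | 270-275 |
| 16 | 316 | 5.1% | 85.4% | 285 | 270-284 |
| 33 | 333 | 9.9% | 81.1% | 300 | 270-299 |
| 34 | 334 | 10.2% | 80.8% | 301 (impossible) | 270-300 |

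For *k* = 33 the best possible wide result is 300/333 = 90.1%. For *k* = 34 it is 300/334 = 89.8%, so the criterion fails on the wide denominator even if every completer succeeds.

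**A result well above the threshold.** With 285 of 300 completers succeeding, the narrow figure is 95.0%. The wide figure is 285/315 = 90.5% with 15 non-completers (pass) and 285/320 = 89.1% with 20 (fail).

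**Where it makes no difference.** If fewer than 270 completers succeed, both readings fail. At 1-2% non-completion (*k* = 3 to 6) the verdict changes only for 270 to at most 275 successes; 275/300 = 91.7%, so completer success must lie between 90% and just under 92%.

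**The case against.** The best counter-argument is that the plain words already favour the wide reading. Section 10.0 says enrolled, the protocol elsewhere uses a different phrase for the analysable 300, and a child excluded post hoc has by then been enrolled. This has real force, and it rules out a stronger claim that a reader might infer: that the protocol definitely drops these children from the feasibility criterion, or conceals them. It does neither. Inability is recorded, the excluded are documented in the final analysis, and both percentages could be worked out if the counts are reported. What remains is that Section 5.3 excludes from the study without limiting this to the accuracy analysis, so the narrow reading is also literal, and a count reported beside a pass does not settle which rule gives the pass.

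Section 5.3 also has exclusions decided before the scan results are reviewed. That guards the accuracy estimates. It does not guard feasibility, because inability to be scanned is both the reason for exclusion and the feasibility outcome.

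The denominator could be left to a statistical analysis plan, which is not at hand. But the protocol itself states the threshold and the exclusion, and it is these two that need reconciling.

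Three limits stand. The protocol's stated purpose and primary outcome concern detection, and it ties no further decision to the 90%. The removal covers only lack of cooperation; slow or repeated completed scans count as failures on either reading. Children excluded for disclosed results or an incomplete eye examination may be scan successes, and keeping them in the wide denominator would shift the ranges in the table.

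**Conclusion.** The point holds as an unresolved conflict between an exclusion rule and an acceptance criterion. One literal reading lets feasibility be declared met however many children could not be scanned, provided at least 270 of the 300 completers meet both limits. The other counts those children as failures. The protocol does not say which applies.

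The size depends wholly on a non-completion rate that the protocol does not give. The effect is small at 1-2%. At about 5% it reverses the verdict for completer success from 90% to just under 95% (284/300 = 94.7%). Above 10% it is decisive for any narrow pass. These figures assume exactly 300 completers and no other exclusions. The point concerns the feasibility conclusion only and makes no claim about the sensitivity or specificity estimates. It is worth correcting because feasibility is a named aim of this phase with a single acceptance rule, and the correction is cheap.

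**What to change.** - **Section 10.0:** define the feasibility denominator as all consented, eligible children brought to PVS testing, including those who refuse or cannot cooperate once testing is begun or offered. Count inability to complete the scan as not meeting the criterion. A denominator of attempted scans alone would not be enough, since a child who refuses at the outset might be said never to have been attempted.
- **Section 5.3:** state that the post-hoc exclusions apply to the accuracy (sensitivity and specificity) cohort only, with the target of 300 unchanged. State also that children excluded for disclosed results or an incomplete eye examination stay in the feasibility denominator with their actual scan result.

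The cost is a few sentences of text and no extra recruitment. Section 5.3 already has inability recorded, and Section 11.0 already provides the rest: "Data forms will be completed for each PVS screen. Key data collected include PVS binocularity score and total time spent testing". The downside is that the feasibility figure may be less favourable.

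### Section 5.3 drops and replaces children who will not cooperate with the scan, so the planned accuracy figures describe completers only, although the stated aim is performance in a primary-care clinic

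*Protocol*

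**What the plan says.** Section 5.3 deals with a child "unable to complete the PVS scan due to lack of cooperation". The inability is recorded and "the participant will be excluded from the study, post-hoc, and not considered a part of the 300-participant cohort". Section 6 continues to invite children "until 300 participants have been enrolled and are eligible for analysis", so each excluded child is replaced.

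Section 5.3 has two safeguards. On reporting: "All excluded participants will be documented in the final analysis to compare how many participants were unable to perform the screening". On timing: "Post-hoc exclusions at this stage will be determined by the study coordinator prior to review of the PVS screening results".

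Section 12 gives the aim: "This second phase is to determine the sensitivity and specificity of the device and its feasibility for widespread deployment in a primary care setting". Section 2.1 likewise places the assessment in a working pediatric clinic, in children from 2 up to 6 years. Section 12 then derives its expectations from 300 children: 5% prevalence, 15 to 20 cases, 14 to 18 of them identified, and at most 45 false referrals. Its starting point is this: "The current published data on PVS sensitivity and specificity is 97% and 87% respectively". It allows 5 points below each, that is 92% and 82%.

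Section 4.1 gives the device two outputs, pass and refer. No section says how a scan that was never obtained enters sensitivity, specificity or false referrals.

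**The concern.** At ages 2 to 5, refusing to cooperate is part of how a screening test behaves in a clinic. A child who cannot be scanned has no result, yet the clinic must still do something with that child. If the child is sent on, referrals go up. If not, an affected child may be missed. Section 5.2 makes a related point itself: affected children without outward signs go unreferred when they are not tested.

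The planned estimates contain neither outcome. They answer how accurate the device is once a scan has been obtained. That is a legitimate question, but narrower than the one in Sections 2.1 and 12. If the completer figures are carried over to a clinic population, referral load or missed cases will be understated, depending on how unscanned children are handled. A count of exclusions shows how many children are missing but not how many of them had amblyopia or strabismus.

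**Working it through.** **Inputs from Section 12:** 300 children, 5% prevalence (15 affected, 285 unaffected), anticipated sensitivity 92% and specificity 82%, published values 97% and 87%.

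**Assumed:** the share u of children who cannot complete the scan. The documents give no value, so 5% and 10% are illustrations. At first u is taken as equal in affected and unaffected children.

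**The plan's own figures.** Cases identified: 15 × 0.92 = 13.8 and 20 × 0.92 = 18.4, which reproduces 14 to 18. False referrals: 285 × 0.18 = 51.3 at 82% specificity and 285 × 0.13 = 37.1 at 87%. The ceiling of 45 matches neither; it implies 1 − 45/285 = 84.2%. That is a separate matter, and the baseline below is 51.

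**Restoring the unscanned children**

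- Counted as refer: sensitivity = (1 − u) × sens + u; specificity = (1 − u) × spec.
- Counted as pass: sensitivity = (1 − u) × sens; specificity = (1 − u) × spec + u.
- False referrals per 300 screened = 285 × (1 − specificity).

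From 92% and 82%:

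| u | Rule | Sensitivity | Specificity | False referrals per 300 | Sens + spec − 1 |
|---|---|---|---|---|---|
| 0 | – | 92.0% | 82.0% | 51 | 0.740 |
| 5% | refer | 92.4% | 77.9% | 63 | 0.703 |
| 5% | pass | 87.4% | 82.9% | 49 | 0.703 |
| 10% | refer | 92.8% | 73.8% | 75 | 0.666 |
| 10% | pass | 82.8% | 83.8% | 46 | 0.666 |

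The last column is 0.740 × (1 − u) under either rule: 0.740 × 0.95 = 0.703 and 0.740 × 0.90 = 0.666.

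**Denominator.** Reaching 300 completers takes 300/(1 − u) = 316 or 333 children. Under the refer rule the totals are 51.3 + 0.95 × 15.8 = 66 among 316 and 51.3 + 0.95 × 33.3 = 83 among 333. These cannot be set against 51 among 300; the comparable figures are 63 and 75.

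**From the published 97% and 87%.** The 5-point allowance is used up when 0.97 × (1 − u) = 0.92, so u = 5.2% (sensitivity, pass rule), or when 0.87 × (1 − u) = 0.82, so u = 5.7% (specificity, refer rule).

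**Unequal failure rates.** Let u_a and u_n be the rates in affected and unaffected children. From 92% and 82%, the sum of the two measures changes by 0.08 u_a − 0.82 u_n under refer, and by 0.18 u_n − 0.92 u_a under pass. It would rise only if affected children failed more than 0.82/0.08 = 10.25 times as often (refer), or unaffected children more than 0.92/0.18 = 5.1 times as often (pass).

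**The case against.** Much can be said for the plan, and several stronger readings do not survive it.

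- **A reader might infer that both measures are overstated.** They are not, at these rates. Each counting rule lowers one measure and slightly raises the other, as the table shows. Taking the specificity loss from one rule and the sensitivity loss from the other would describe no actual clinic.
- **A reader might take 10% from the feasibility criterion in Section 10.** That criterion concerns time under 2 minutes and fewer than 3 attempts. A child scanned slowly or on the third try misses it but remains in the 300. It is not a scan-failure rate. At 5%, the losses from 92% and 82% are 4.6 and 4.1 points, inside the plan's 5-point allowance.
- **A reader might infer that every failed scan is removed.** Section 5.3 names lack of cooperation; it does not mention technical failure.
- **A reader might infer that disease status is lost.** The text does not say so. The exclusion is post hoc, no section cancels the eye examination, and Section 10 plans a cycloplegic refraction for all children. The protocol is silent for excluded children, which is a gap and not proof of loss.
- **Specificity can nearly be checked from the count alone.** At 10% failure, with prevalence among failures anywhere from 0 to 10%, refer-rule specificity lies between 233.7/315.0 = 74.2% and 233.7/318.3 = 73.4%. Sensitivity needs the examination, but only about 0.8 to 1.7 cases are expected among the failures (5% of 15.8 or 33.3).
- **The safeguards have value.** Deciding exclusions before results are reviewed limits result-driven exclusion, and the count will be visible. The extra analyses could also sit in a statistical analysis plan, which is not at hand.

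These points narrow the finding but do not remove it. The exclusion and replacement rules are in the protocol, and an analysis plan cannot supply examinations that were not done.

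**Conclusion.** The point holds in a limited form. As written, the accuracy estimates are conditional on a completed scan, while the stated aim concerns a clinic population that includes children who will not cooperate. Reporting the number excluded does not bring them into any accuracy figure.

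Under equal failure rates, overall discrimination is overstated because sensitivity + specificity − 1 shrinks by the factor (1 − u). Which single measure suffers depends on what happens to an unscanned child, and the protocol does not fix that. At an assumed 5% to 10%, the loss is 4.1 to 8.2 points of specificity or 4.6 to 9.2 points of sensitivity. The rates are assumptions, and the true size cannot be calculated from the documents.

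The sensitivity shift should also be read against its imprecision: 14 of 15 has an exact 95% interval of about 68% to 99.8%. This is an inexpensive improvement worth making, not a flaw that invalidates the completer estimates.

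**What to change.** 1. Amend Section 5.3 so that a child who cannot complete the scan stays in the study, is recorded as 'scan not obtained', and has the already planned eye examination where he or she can complete it.
2. Keep recruiting to 300 completers for the planned estimates, and label those estimates 'among children with a completed scan'.
3. Add sensitivity and specificity over all enrolled and examined children, once with failures counted as screen-positive and once as screen-negative. Show both measures under each rule, and give false referrals per fixed number screened.
4. Report how many children without a scan could not be examined either.

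The two counting rules are analysis bounds and do not settle how a clinic should manage such a child.

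The cost is a wording change, two further analyses, and some examinations in children who are also replaced: about 16 to 33 at the assumed rates, and extra only if these children would not have been examined anyway. Some who refuse the scan may refuse the examination too, so the all-enrolled figures may be incomplete for this group. They will also look less favorable.
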